This research addresses the following "big-picture" questions: "Is the density notification law recently adopted in AZ having the intended impact on patients receiving mammography at a Federally Qualified Health Center (FQHC)?" and "Are there positive or negative unintended consequences to this legislation?" We hypothesize that sending standard-language (as determined by legislators) notification about breast density along with a woman's mammogram results is a sub-optimal method of notification. Further, we hypothesize that the goals of educating women about their breast density, (including the impact that dense breast tissue can have on mammogram sensitivity and overall risk of breast cancer) and encouraging a discussion with their health care provider about breast cancer screening options, may not be achieved by sending written notification in the absence of additional efforts to educate women about breast density. We propose to answer these questions by conducting a 3-arm randomized trial. All arms will receive the standard density notification letter, but 2 arms will also receive educationally-enhanced notification about breast density. Thus, the 3 study arms are:

usual care (standard density notification only), enhanced (standard density notification + written educational materials on breast density), and interpersonal (standard density notification + written educational materials on breast density + verbal interaction with a *promotora*/health educator).

The impact of this research can only increase as additional states mandate that women attending mammography screening (many of whom have never heard of breast density before) receive written notification about their breast density and its role in breast cancer risk. Particularly in FQHC's and other community settings where breast imaging experts may not be on staff and patients may have limited English proficiency, lower health literacy, and fewer economic resources, it is critical that density notification occur in ways that optimize receptivity and comprehension, minimize anxiety and worry, and enhance self-efficacy and intention to continue screening and pursue supplemental breast screening, if appropriate.

Aims, purpose, or objectives:

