Specific Aim 1: Compare anxiety as well as knowledge gained between breast density notification approaches (usual care, enhanced, interpersonal). We hypothesize that Latinas randomized to the interpersonal group (receiving a density notification letter that is accompanied by written educational materials, plus interaction with a *promotora*) will have less anxiety and more knowledge gained relative to either the usual care or enhanced study groups.

Specific Aim 2: Compare adherence to next routine screening mammogram between breast density notification approaches (usual care, enhanced, interpersonal). We hypothesize that Latinas randomized to the interpersonal group (receiving a density notification letter that is accompanied by written educational materials, plus interaction with a *promotora*) will be more likely to adhere to next screening mammogram relative to either the usual care or enhanced study groups.

Specific Aim 3: Whether or not the interpersonal group is found to have more favorable outcomes, we will examine the experience of the *promotora* in order to understand their conversations with patients, identify patients' concerns about their notification, and understand contextual factors related to implementation of the intervention. If the interpersonal approach is found to be successful, this aim will inform refinement of the educational intervention for dissemination; if the interpersonal approach is not found to be successful, this aim will provide insight about potential shortcomings. This aim will involve qualitative inquiry.

Exploratory Aim 1: Estimate the financial impact of the *promotora* intervention by performing a cost analysis

Exploratory Aim 2: Examine the association between perceived BC risk and preferences for informed decision making. We hypothesize that Latina women with a higher perceived risk will report a greater desire for involvement in the decision to get a mammogram and more likely to report that they made the final decision to get mammography.

Exploratory Aim 3. Examine the association between risk communication and preferences for informed decision making. We hypothesize that Latina women interested in knowing their risk will report a greater desire for involvement in the decision to get a mammogram and more likely to report that they made the final decision.

Background (*Include relevant experience, gaps in current knowledge, preliminary data, etc.*):

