This study will utilize our prior research experience at MPHIC and apply the knowledge that we learned conducting the national survey study. In short, we are well-prepared to conduct the proposed study. Mandatory notification imposed by legislation is gaining momentum in the absence of empirical data regarding its potential effect on women, which are assumed to be positive. Moreover, notification is gaining momentum in the absence of clear guidelines regarding appropriate supplemental screening for women with dense breast tissue and counseling regarding breast cancer risk. We

propose to conduct a randomized trial to compare behavioral and psychological outcomes among Latinas who receive notification per the mandate (usual care) relative to two enhanced approaches that are theory informed, culturally consistent, and novel in this context. Our findings will fill critical gaps in our knowledge and understanding of how this policy affects women who are already vulnerable to disparities. It will provide evidence on the feasibility and efficacy of a portable intervention to increase knowledge of breast density, and be able to determine approximate costs of intervention delivery in a FQHC setting.

Study Design and Methods

Methods: *Describe, in detail, the research activities that will be conducted under this protocol:*

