Adherence to subsequent mammography screening or follow-up testing (diagnostic mammography, breast ultrasound), and delay in attending follow-up care will be ascertained from the EMR. We will record attendance (yes or no) at screening mammography 1 and 2 years following study enrollment. As recommended screening intervals differ by major consensus groups and may be annual or biennial, patient adherence to recommended screening interval will be determined based upon review of the clinic note. Presently, MPH follows annual screening guidelines starting at age 40. Further, we will examine timeliness in returning for follow-up among women who are recalled for an abnormal mammogram, as delays in diagnosis may contribute to disparities in breast cancer outcomes. Specifically, we will record the number of weeks of delay in attending a follow-up appointment as a "time to adherence" variable; women who are adherent will be assigned a delay score of "0." It has been shown that delays in diagnosis of breast cancer as short as 3 months are associated with decreased survival, therefore we will also consider delay as a dichotomous variable: follow-up of an abnormal screening mammogram was received within 3 months of the scheduled appointment (not delayed) or sometime thereafter (delayed). Any uptake in supplemental breast screening among women with dense breasts will be captured in the EMR review.

Women will be compensated a maximum of \$100 upon completing this study. They will be given \$25 upon completion of the T1 (baseline) assessment, \$25 upon completion of the T2 assessment, \$25 upon completion of the T3 assessment, and \$25 upon completion of the T4 assessment.

Aim 3 Data Collection. Subsequent to completing the delivery of the interpersonal intervention with a patient [Attachment 14], the *promotora* will complete a form with open- and close-ended questions about the encounter [Attachment 15]. It will document standard information related to the conversation, such as what questions the patient asked and whether there were issues the *promotora* was unable to address, as well as serve as self-reported information on intervention delivery adherence. Once every 1-2 weeks, the *promotora* will respond to a set of longer, reflective questions

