The study will employ a *promotora* who is also staff at MPH and who is familiar with the patient population, clinic setting, language, and culture of the study population. She will undergo careful training in the delivery and documentation of each interaction in which breast density results are discussed with study patients. Training by Co-I [name] will ensure that the *promotora* is knowledgeable about MBD, can respond factually to patient questions, and defer questions appropriately to the patient's health care provider. Training by [name] and [name] will ensure that the *promotora* fully appreciates the need for consistent delivery of the information as part of a research protocol, including documenting departures from protocol. When the *promotora* calls each patient, the following material will be available: the mammogram report, the density notification letter, and a written "interaction guide" that is based on factual information about MBD and tailored to the language and literacy appropriate for this setting. With patient permission, calls may be audio-recorded for monitoring by the PI to evaluate fidelity of the intervention and verify documentation by the *promotora* after the call. We will record at least 50% of the encounters during the first month of *promotora* intervention delivery or until 20 cases have been recorded. Two members of the study team will review the audio files and complete a checklist with adherence items (presence or absence of intervention components outlined in the interaction guide) as well as ratings of intervention delivery competence based on program theory [Attachment 17]. The expected performance level will be at least 95% on the adherence items. Retraining will take place if lower performance is found. The fidelity checklist will also be reviewed at the end of this case review and any necessary changes will be made before instituting long-term fidelity monitoring.

Long-term monitoring will begin when the 95% performance measure is met. From that point on we will randomly sample 20% of *promotora* interactions over the course of the study and the two observers will compare results monthly. If performance falls below 95%, we will address reasons and sample at 50% again until performance improves.

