to the narrative data, which will be indexed using NVivo (NVivo 10, QSR International Pty Ltd.). All NVivo datafiles are housed behind the Mayo Clinic firewall. Subsequently, the research team will review the audio-recorded *promotora*-patient interactions and apply the analytic framework to them using NVivo in order to triangulate the perspective of the *promotora* and observation of the intervention's delivery by the study team.

Analytic Approach for Exploratory Aim 1

There are no standard approaches to performing a financial evaluation of *promotora* interventions; a systematic review identified only 6 studies that provided economic analyses of community health worker interventions, with insufficient evidence to conclude a cost benefit. The time spent by the *promotora* contacting and educating each patient randomized to the interpersonal study group about her breast density results will be recorded, and the mean *promotora* time per patient will be estimated. The prevailing hourly salary plus benefits will be used to estimate the mean cost of *promotora* time per patient.

Analytic Approach For Exploratory Aims 2 and 3

We will test each hypothesis using multivariate regression analyses, adjusting for relevant confounders. We will also explore differences in perceived risk, risk communication, and preferences for informed decision-making using chi-square tests.

List of Attachments (Documents to be found in IRBe)

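### The cost analysis prices only the promotora's time, so its result is a lower bound on the delivery cost that the protocol says it will determine

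*Combined protocol and SAP*

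**What the plan says.** Two places in the combined protocol and SAP say what the cost work will deliver:

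- Exploratory Aim 1, in the list of aims: "Estimate the financial impact of the" promotora intervention, by means of a cost analysis.
- The closing paragraph of the Background: the study will "be able to determine approximate costs of intervention delivery in a FQHC setting".

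One place says how this will be done. The Analytic Approach for Exploratory Aim 1 has the promotora's time recorded for each woman in the interpersonal arm and averaged, and then: "The prevailing hourly salary plus benefits will be used to estimate the mean cost of" that time per patient. It lists no other resource, unit price or comparator.

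Two further places describe what delivery consists of:

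- The opening statement of the research question defines the third arm as "interpersonal (standard density notification + written educational materials on breast density + verbal interaction with a" promotora, and the second arm as "enhanced (standard density notification + written educational materials on breast density".
- The Resources section says of the promotora: "She will undergo careful training in the delivery and documentation of each interaction". It also provides for retraining when performance on the adherence items falls below 95%.

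**The concern.** The aim and the Background speak of the intervention and its delivery. The method costs one input, labour during patient contact. A health center weighing adoption of the interpersonal approach would also have to obtain the written materials and prepare a promotora to deliver the content. If the labour figure is reported under the heading of Exploratory Aim 1, it will tend to be read as the cost of the whole approach and will be too low for that purpose.

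What is at stake is the completeness of one descriptive estimate. Aims 1 to 3, their tests and their error control do not depend on it.

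**Working it through.** The documents state no cost figure, so there is nothing to reproduce. The check sets the components of delivery against the items priced.

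**Step 1. Components against prices**

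| Component of interpersonal delivery | Where described | Priced in the Exploratory Aim 1 method? |
|---|---|---|
| Promotora time contacting and educating women | Analytic Approach for Exploratory Aim 1 | Yes |
| Written education materials | Arm definition, opening statement | No |
| Promotora training needed for delivery | Resources | No |
| Retraining, if it occurs | Resources | No |

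**Step 2. Direction.** Define:

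- h = mean promotora hours per woman, and w = hourly salary plus benefits
- M = cost of written materials per woman
- K = total cost of delivery-related training and retraining
- N = number of women over whom K is spread

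Planned figure: h × w.

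Delivery cost per woman with the described components: h × w + M + K/N.

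Shortfall: M + K/N. Both terms are zero or positive, so the planned figure is a lower bound.

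**Step 3. Size.** Of these quantities the documents supply only a natural value for N within the trial. The Power Statement gives about 667 women per group, which agrees with 2,000 / 3 = 666.7. No values are given for h, w, M or K, so neither M + K/N nor its ratio to h × w can be calculated.

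**Step 4. Dependence on the comparator.** Materials go to both the enhanced and the interpersonal arms. Writing the cost differences with the same symbols:

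- Interpersonal minus enhanced: h × w + K/N. M cancels, and the planned figure is short by K/N.
- Interpersonal minus usual care: h × w + M + K/N. Nothing cancels, and the planned figure is short by M + K/N.

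Training is therefore missing from either contrast. Materials are missing from the contrast with usual care and from the total delivery cost.

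**The case against.** The best defence is that the method describes its own output honestly, as a cost of promotora time. The Background promises only approximate costs, the aim is exploratory, and the analytic section itself says that no standard approach exists. The promotora contact is also what distinguishes the interpersonal arm from the enhanced arm. All of this stands, and it is why the point is minor. It does not close the gap: a correctly labelled labour cost still does not answer an aim about the intervention or a claim about delivery. The lack of a standard method is a reason to list what is included.

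A second defence is that some of the omitted effort belongs to the research. This is partly right. Some of the training in Resources concerns consistency under a research protocol, and retraining is triggered by the study's own monitoring. Whether a clinic would bear the retraining cost is a judgement, which favours showing it as its own line.

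A reader might also infer more than the documents support:

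- **That time spent on women who are never reached is lost.** The promotora's encounter form is indeed filled in "Subsequent to completing the delivery of the interpersonal intervention with a patient". But that form is described under Aim 3 data collection, and the costing section says separately that time spent "contacting and educating each patient randomized to the interpersonal study group about her breast density results will be recorded". Its wording covers contact time for every woman assigned to the arm. At most, the recording instrument is not named in the visible text.
- **That supervision and postage are omitted components.** Resources describes fidelity monitoring by the study team, which is not the same as supervision that a clinic would need. No section says the education materials are mailed separately from the notification letter, which every arm receives.
- **That the plan fails to give a cost per additional adherent woman.** The plan never proposes a cost-effectiveness ratio, so its absence is not a defect.

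**Conclusion.** The concern holds in limited form. Read against Exploratory Aim 1 and the Background, the planned figure leaves out the written materials and delivery-related training and retraining, and so is a lower bound on delivery cost. The direction rests on one assumption, that the omitted items cost something. The size is undetermined. A reader might be tempted to put a percentage on it, but apart from the 667 women per group every input would have to be assumed, and the result would only restate those assumptions. Even 667 is a choice, since an adopting clinic would spread training over its own patient volume.

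The documents do not support saying that the trial's result would mislead, given how the output is labelled. Severity is minor, because only a descriptive exploratory aim is affected.

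**What to change.** In the Analytic Approach for Exploratory Aim 1, report the promotora time cost as planned and add, per woman randomized to the interpersonal arm:

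1. a line for the written education materials;
2. a line for delivery-related training, and a separate one for any retraining, with the number of women over whom each is spread. Giving the total as well would let a clinic rescale it.

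Leave out research-only activity: training specific to the research protocol, the two-person review of recordings, and the promotora's reflective diary. Note beside the table that the materials cost cancels against the enhanced arm but not against usual care.

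If these lines are not added, reword Exploratory Aim 1 and the Background claim so that both refer only to the cost of promotora contact time.

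The cost is a few lines drawn from the study budget. The drawback is a less favourable cost per patient.
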